#### 18.4.2. MARKEDLY ABNORMAL CRITERIA VITAL SIGNS (MAPVS)

Markedly abnormal post-baseline Vital Signs (MAPVS) will be identified in accordance with the following predefined markedly abnormal criteria

Variable (unit)	Low	High
SBP (mmHg)	≤ 90 mmHg AND change from baseline ≤ -20 mmHg	≥ 180 mmHg AND change from baseline ≥ 20 mmHg
DBP (mmHg)	≤ 50 mmHg AND change from baseline ≤ -15 mmHg	≥ 105 mmHg AND change from baseline ≥ 15 mmHg
Respiratory rate (breaths/ minute)	≤ 10 breaths/minute AND Percentage change from baseline ≤ - 50% breaths/minute	≥ 25 breaths/minute AND Percentage change from baseline ≥ 50% breaths/ minute
Pulse rate (bpm)	≤ 50 bpm AND change from baseline ≤ -15 bpm	≥ 120 bpm AND change from baseline ≥ 15 bpm
Body temperature (c)	NA	≥ 38.3 °C
Weight (kg)	percentage change from baseline ≤ - 7.0 %	percentage change from baseline ≥ 7.0 %

### 18.5. PHYSICAL EXAMINATION

The clinically significant abnormalities or changes which are noted in the physical exams are recorded as part of medical history (if noted during screening) and as adverse events at other timepoints. Their summaries/listings are thus included in the medical history and adverse events outputs.

A listing displaying whether a physical examination was performed for each subject and the date of the physical examination. OSAF population will be used.

---

Document:

Author:

Version Number:  
Version Date:

Final Draft  
11APR2019

Template No: CS\_TP\_BS016 Revision 4  
Effective Date: 01Apr2016

Reference: CS\_WI\_BS005

## 18.6. OTHER SAFETY ASSESSMENTS

### 18.6.1. INVESTIGATOR INJECTION SITE ASSESSMENTS

The Investigator will assess the injection site using a rating of Grade 1-4 on each of the 4 items (pain, tenderness, erythema/redness, and induration/swelling).

ISAF population will be used for all investigator injection site reaction summaries.

Injection site reactions will be assessed for severity according to each of the following categories (per the Investigator's judgement):

Local Reaction to Injectable Product	Mild (Grade 1)	Moderate (Grade 2)	Severe (Grade 3)	Potentially Life Threatening (Grade 4)
Pain	Does not interfere with activity	Repeated use of non-narcotic pain reliever > 24 hours or interferes with activity	Any use of narcotic pain reliever or prevents daily activity	Emergency room (ER) visit or hospitalization
Tenderness	Mild discomfort to touch	Discomfort with movement	Significant discomfort at rest	ER visit or hospitalization
Erythema/Redness	2.5 – 5 cm	5.1 – 10 cm	> 10 cm	Necrosis or exfoliative dermatitis
Induration/Swelling	2.5 – 5 cm and does not interfere with activity	5.1 – 10 cm or interferes with activity	> 10 cm or prevents daily activity	Necrosis

The following summaries will be provided for investigator injection site assessment data.

- Proportion of subjects with mild, moderate, severe, life-threatening, and any severity of each of the four injection site reaction assessments by treatment and scheduled timepoint.
- Data listing of investigator injection site assessment.

---

Document:

Author:

Version Number:  
 Version Date:

Final Draft  
 11APR2019

Template No: CS\_TP\_BS016 Revision 4  
 Effective Date: 01Apr2016

Reference: CS\_WI\_BS005

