- n Investigator injection site safety assessment will include a rating of 1-4 on each of 4 items (pain, tenderness, erythema/redness, and induration/swelling). Assessments will be made on Day 1 (immediately after injection, and 6 hours and 12 hours after injection), Day 2 (24 hours after injection), Days 3-15 (daily during the inpatient period), Day 22, and Day 29. A window of +1 minute is allowed for the immediately after injection timepoint, and a window of ± 5 minutes is allowed for the 6 and 12 hour timepoints on Day 1. In addition subjects will be monitored for potential allergic reaction for 15 minutes after injection. A window of 0-5 minutes is allowed for the evaluation of potential allergic reaction.
- ^o Subjects will assess their injection site pain using a rating of 0-10 on a Likert Scale (0 = no pain, 10 = worst pain). This assessment will be completed prior to the Investigator injection site assessment on Day 1 (immediately after injection, and 6 hours and 12 hours after injection), Day 2 (24 hours after injection), Day 8, Day 15, Day 22, and Day 29. A window of +1 minute is allowed for the immediately after injection timepoint, and a window of ± 5 minutes is allowed for the 6 and 12 hour timepoints on Day 1.
- P Alternate subjects not included in the study cohort will be discharged following reintroduction of their prior medication if they are clinically stable (in the Investigator's opinion), subjects who received study drug will be eligible for discharge on Day 15 (but may remain inpatient at the Investigator's discretion up to Day 33), and early withdrawal subjects will be discharged after follow-up assessment procedures.
- ^q Concomitant medications will be recorded prior to and after oral and injection dosing.
- ^r In addition to any untoward medical occurrences in the subject (pre and postdose on dosing days), assessment of the injection site and monitoring of prodromal symptoms for seizures will be performed. If prodromal symptoms for seizure are found, additional neurological assessments will be done, as needed.

TABLE OF CONTENTS

RESTR	ICTED DISTRIBUTION OF PROTOCOLS	2
EMERO	GENCY CONTACTS	3
1.	SYNOPSIS	4
2.	LIST OF ABBREVIATIONS AND DEFINITIONS OF TERMS	22
3.	INTRODUCTION	25
3.1.	Background	25
3.2.	Study Conduct Rationale	26
3.3.	Risk-Benefit Assessment	26
4.	STUDY OBJECTIVES	26
4.1.	Safety Objective	26
4.2.	Pharmacokinetic and Pharmacodynamic Objectives	26
5.	STUDY ENDPOINTS	27
5.1.	Safety Endpoints	27

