5. STUDY ENDPOINTS

5.1. Safety Endpoints

- Incidence of AEs, serious adverse events (SAEs), and AEs leading to study discontinuation
- Incidence of injection site-related reactions, including injection site pain, injection site erythema, injection site induration, injection site ulcer, injection site granuloma and injection site swelling
- Observed values and changes from baseline in clinical laboratory tests (hematology, serum chemistry, urinalysis, coagulation, and liver function), vital signs (respiratory rate, body temperature, supine blood pressure, and pulse), orthostatic effects (based on blood pressure and pulse rate), and 12-lead electrocardiograms (ECGs) parameters
- Incidence and severity of subjects with suicidal ideation or suicidal behavior using the Columbia-Suicide Severity Rating Scale (C-SSRS)

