6.3.2. Rationale for the Dosages

Dosing for the lurasidone injectable suspension formulation is based on the amount in mg of lurasidone present at the injection site following IM administration, which was $\sim\!60$ mg at the lowest dose of 7.5 mg/kg in the dog. There was no no-observed-adverse effect level determined in the dog; therefore a 2-fold reduction in the amount of lurasidone at the injection site was recommended, which is equal to 30 mg. At the clinical formulation's fixed concentration of 150 mg/mL, this dose will be an injection volume of 0.2 mL.

A 2-fold reduction is considered appropriate because the primary finding of granuloma is common following IM administration of an irritating substance. Clinicians are familiar with appropriate monitoring. This finding is reversible and non-lethal. The pharmacology of lurasidone is well known, and systemic findings in humans have been characterized over a range of serum concentrations.

After the lurasidone injectable suspension starting dose of 30 mg, dose escalation will be as follows: 75, 150, 300, 450 mg for a single IM injection. A 6 week monitoring period for adverse events will be employed in this study. In animals, the injection site findings were apparent within 1 week and findings persisted for an additional week before beginning to resolve. Therefore, if no injection site findings are seen within 2 weeks and no other stopping criteria are met, dose escalation may proceed.

Projection of PK following each cohort indicates that C_{max} will not exceed 348 ng/mL. This value is the C_{max} at 400 mg orally, which is the MTD (Study D1050217, Day 6). It is unlikely that IM administration will exceed this concentration as the depot will absorb more slowly than following oral administration. Therefore, routine safety monitoring will be utilized to determine stopping criteria.

In order to ensure subjects who are unable to tolerate lurasidone do not receive the lurasidone injectable suspension formulation, subjects will be evaluated for tolerability after administration of oral lurasidone 80 mg for 2 days (ie, two doses) prior to lurasidone injectable suspension administration.

The oral lurasidone 80 mg dose was previously established as the maximum tolerated dose (MTD) in healthy subjects. In subjects with schizophrenia, an oral lurasidone dose of 400 mg/day was previously established as the MTD.

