### **3.3. STUDY ENDPOINTS**

#### **3.3.1. SAFETY ENDPOINTS**

Incidence of AEs, serious adverse events (SAEs), and AEs leading to study discontinuation

Incidence of injection site-related reactions, including injection site pain, injection site erythema, injection site induration, injection site ulcer, injection site granuloma and injection site swelling

Observed values and changes from baseline in clinical laboratory tests (hematology, serum chemistry, urinalysis, coagulation, and liver function), vital signs (respiratory rate, body temperature, supine blood pressure, and pulse), orthostatic effects (based on blood pressure and pulse rate), and 12-lead electrocardiograms (ECGs) parameters

Incidence and severity of subjects with suicidal ideation or suicidal behavior using the Columbia Suicide Severity Rating Scale (C-SSRS)

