### **18.6.2. SUBJECT INJECTION SITE PAIN SCORE**

The subject will assess their injection site pain using a rating of 0-10 on a Likert scale (0 = no pain, 10 = worst pain). This will be completed prior to the Investigator's injection site assessment.

ISAF population will be used for all subject injection site pain score summaries.

Subject injection site pain score will be categorized as follows:

- 0 = No pain
- 1-3 = Mild pain
- 4-6 = Moderate pain
- 7-10 = Severe pain

The following summaries will be provided for subject injection site pain score data.

- Descriptive Statistics for the pain score (0-10) by treatment and scheduled timepoint.
- Frequency and percentage of the pain score categories (no pain, mild pain, moderate pain and severe pain) by treatment and scheduled timepoint.
- Data listing of subject injection site pain score.

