Table 14.3.2.2	Adverse Events Leading to Study Discontinuation - Injectable Safety Population
Table 14.3.4.1.1	Serum Chemistry: Actual Value and Change from Baseline by Scheduled Timepoint and Treatment - Injectable Safety Population
Table 14.3.4.1.2	Serum Chemistry: Shift from Baseline by Scheduled Timepoint and Treatment - Injectable Safety Population
Table 14.3.4.2.1	Hematology Parameters: Actual Value and Change from Baseline by Scheduled Timepoint and Treatment - Injectable Safety Population
Table 14.3.4.2.2	Hematology: Shift from Baseline by Scheduled Timepoint and Treatment – Injectable Safety Population
Table 14.3.4.3.1	Urinalysis: Actual Value and Change from Baseline by Scheduled Timepoint and Treatment - Injectable Safety Population
Table 14.3.4.3.2	Urinalysis: Shift from Baseline by Scheduled Timepoint and Treatment - Injectable Safety Population
Table 14.3.4.4	Summary of Markedly Abnormal Post-Baseline Laboratory Value (MAPLV) by Treatment - Injectable Safety Population
Table 14.3.5.1	Vital Signs: Actual Value and Change from Baseline by Scheduled Timepoint and Treatment - Injectable Safety Population
Table 14.3.5.2	Summary of Abnormal Post-Baseline Vital Signs (MAPVS) Values by Treatment - Injectable Safety Population
Table 14.3.5.3	Incidence of Orthostatic Hypotension and Orthostatic Tachycardia by Treatment - Injectable Safety Population
Table 14.3.5.4.1	ECG: Actual Value and Change from Baseline by Scheduled Timepoint and Treatment - Injectable Safety Population
Table 14.3.5.4.2	Summary of ECG Categories of Markedly Abnormal Criteria by Treatment - Injectable Safety Population

Document:

Author:

Version Number:  
 Version Date:

Final Draft  
 11APR2019

Template No: CS\_TP\_BS016 Revision 4  
 Effective Date: 01Apr2016

Reference: CS\_WI\_BS005

Statistical Analysis Plan

PROTOCOL D1052024  
 Page 63 of 66

Number	Title
Table 14.3.5.5.1	Summary of Columbia Suicide Severity Rating Scale (CSSRS) by Scheduled Timepoint and Overall Screening/Baseline and Last Visit Questionnaire - Injectable Safety Population
Table 14.3.5.6.1	Investigator Injection Site Reaction by Treatment and Schedule Timepoint - Injectable Safety Population
Table 14.3.5.6.2	Subject Injection Site Reaction Pain by Treatment and Schedule Timepoint - Injectable Safety Population
Figure 14.2.1.1	Mean (+SD) Lurasidone Serum Concentration-time Profiles by Dose on Linear and Semi-logarithmic Scales - Pharmacokinetic Population

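### The injection-site grades and pain scores are tabulated only by timepoint, so per-subject incidence of local reactions rests on adverse-event reporting alone

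*SAP*

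**What the plan says.** Protocol 5.1 and SAP 3.3.1 list, as a safety endpoint, the incidence of injection-site reactions. The named terms are pain, erythema, induration and then "injection site ulcer, injection site granuloma and injection site swelling". Protocol 14.3.5.7 says the two site instruments will be summarised by treatment and leaves the detail to the SAP.

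- **Investigator scale (SAP 18.6.1).** Four items (pain, tenderness, redness, induration or swelling) are graded 1 to 4. The planned summary is the proportion of subjects at each grade and with "any severity of each of the four injection site reaction assessments by treatment and scheduled timepoint".
- **Subject pain score (SAP 18.6.2).** The 0 to 10 score gets descriptive statistics by timepoint, plus "Frequency and percentage of the pain score categories (no pain, mild pain, moderate pain and severe pain) by treatment and scheduled timepoint".
- **Table list (SAP Appendix 4).** Table 14.3.5.6.1 is "Investigator Injection Site Reaction by Treatment and Schedule Timepoint - Injectable Safety Population", and Table 14.3.5.6.2 has the same layout for pain. Listings 16.2.8.12 and 16.2.8.13 show the individual assessments.
- **Unscheduled data (SAP 7.3).** Unscheduled post-baseline measurements do not enter by-visit summaries.
- **Adverse events.** Protocol 14.3.5.1 counts each subject once per system organ class (SOC) and preferred term (PT). SAP 18.1.1.1 uses the highest severity. SAP 18.1.1 promises summary tables of injection-site reaction events, but the only such table in Appendix 4 is Table 14.3.1.5, on duration.

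**The concern.** Incidence is the share of subjects who have a reaction at any time after the injection. A table by timepoint gives the share who have one on that day. The two agree only if all reactors are reacting together at some assessment. The instrument built for local tolerability is applied on a fixed schedule to everyone, yet it yields no per-subject incidence and no worst grade.

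This matters because local reaction is the toxicity that drives the dose rationale. Protocol 6.3.2 sets the starting dose from the dog injection-site data and says that "the primary finding of granuloma is common following IM administration of an irritating substance". A reader of the final report will want to know how many subjects at each dose had any reaction, and how bad the worst one was. The planned tables of graded data do not answer either question.

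**Working it through.** **Inputs.** Timepoints come from Protocol Table 2, footnotes n and o. Cohort sizes come from SAP 4.1. The documents state no expected reaction rate, onset or duration, so there is no figure of theirs to reproduce; any such value below is an assumption.

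**Step 1: number of rows.**
- Investigator scale: 3 on Day 1, 1 on Day 2, 13 on Days 3 to 15, then Day 22 and Day 29: 3 + 1 + 13 + 1 + 1 = 19.
- Subject pain: 3 on Day 1, then Days 2, 8, 15, 22 and 29: 3 + 5 = 8.

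**Step 2: denominators.** There are 6 active subjects per cohort. With five cohorts, pooled placebo is 5 × 2 = 10.

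**Step 3: what the rows say about incidence.** With complete data at every row, for any item:

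highest row ≤ share of subjects who ever react ≤ min(100%, sum of rows)

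The highest row is a lower bound. Adding rows counts the same subject more than once.

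**Step 4: large-gap end.** If 6 of 6 active subjects each react on a different day, true incidence is 100% and no row exceeds 1/6 = 16.7%. For 10 of 10 pooled placebo subjects the same pattern gives 1/10 = 10%.

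**Step 5: the range for a given row value.** Suppose every row shows proportion p. If the same subjects react throughout, incidence is p. If timepoints were independent, it is 1 − (1 − p)^k.

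| p per row | Same subjects throughout | Independent, k = 8 | Independent, k = 19 |
|---|---|---|---|
| 5% | 5% | 34% | 62% |
| 10% | 10% | 57% | 87% |

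Neither end is realistic. The point is that the tables cannot distinguish them.

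**Step 6: no-gap end.** Protocol 6.3.2 reports that animal findings appeared within a week and persisted about another week. If that carried over, with onset on Days 2 to 8 and duration of at least 7 days, every reaction would be present on Day 8. The Day 8 row would then be 6/6 = 100% when all react.

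**Step 7: how the SAP handles other safety data.**

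| Domain | Per-subject count across the post-injection period | Place |
|---|---|---|
| Laboratory, markedly abnormal | Yes, unscheduled included | SAP 18.2, 7.3 |
| Vital signs, markedly abnormal | Yes, unscheduled included | SAP 18.4, 7.3 |
| ECG criteria | Yes, overall injection period, unscheduled included | SAP 18.3 |
| C-SSRS | Yes, any time during treatment | SAP 18.6.3.1 |
| Adverse events | Yes, highest severity | SAP 18.1.1.1 |
| Investigator site grade | None | SAP 18.6.1 |
| Subject pain score | None | SAP 18.6.2 |

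**Step 8: what the adverse-event route supplies.** It gives per-subject counts by SOC and PT, on the mild, moderate, severe scale of Protocol 11.3. It does not use the four-grade, partly size-based scale of Protocol 9.3, and no text says when a graded finding becomes an adverse event. No listed table gives the number of subjects with any injection-site reaction. Summing preferred terms would count a subject with two terms twice.

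**The case against.** The strongest reply is that nothing ties the endpoint to the graded scale. The endpoint list omits tenderness, which the scale rates, and includes ulcer and granuloma, which it does not. It reads like a list of adverse-event terms, and the adverse-event tables do count each subject once per term at highest severity. On that reading the endpoint has an analysis, and a worst grade is an addition to it. With 6 active subjects per cohort and descriptive safety analyses, a reader could also take each subject's worst grade from Listing 16.2.8.12.

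Most of this stands, and it limits the point. A reader might infer from the by-timepoint tables that the trial will understate incidence. The documents do not support that: those tables do not claim to report incidence, the adverse-event tables are a separate route, and the animal time course could leave no gap at all.

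A reader might also infer that a granuloma would be missed unless the subject volunteered it. That does not hold either. The investigator examines the site on a schedule through Day 29, and Table 2 footnote r includes site assessment in adverse-event monitoring. Physical examinations continue to Day 61, and Protocol 10.2.3 and 11.2 direct changed or clinically significant findings into adverse-event records.

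What the reply does not remove is that a count made by hand from a listing is not prespecified, and that the adverse-event route has neither a composite incidence table nor a stated term list.

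**Conclusion.** The point holds as a gap in the planned summaries. The graded investigator data and the pain score give point prevalence only, and the highest row is a lower bound on the share of subjects who ever react. The shortfall runs from zero, when reactions are long and overlap, to a highest row of 1/6 against a true 6/6 when they are brief and scattered. Where it will fall cannot be known beforehand, because the documents give no human onset or duration. Per-subject incidence therefore rests on adverse-event reporting, without a stated mapping from the graded findings and without an injection-site incidence table.

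The absence of granuloma and ulcer items from the scale might suggest that new form entries are needed, including after Day 29. The documents do not establish that need. Table 2 ends the site form at Day 29, and later findings have the physical-examination and adverse-event route. What is needed is for both terms to be named in the adverse-event analysis.

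**What to change.** 1. Add a worst post-injection block to Tables 14.3.5.6.1 and 14.3.5.6.2, including unscheduled assessments. Give the number and percentage of subjects by highest investigator grade, for each item and for any item, and by highest subject pain category, for each dose and pooled placebo. Because the investigator scale starts at Grade 1, include a line for subjects with no graded reaction.
2. Add one injection-site adverse-event incidence table in the injectable safety population, with a row for any reaction and rows by preferred term. Prespecify the term list and include granuloma and ulcer in it.

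The cost is one derived maximum per subject and one extra adverse-event table. No visit, form or procedure changes, and the by-timepoint rows stay as they are to show the time course.

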### **18.6.2. SUBJECT INJECTION SITE PAIN SCORE**

The subject will assess their injection site pain using a rating of 0-10 on a Likert scale (0 = no pain, 10 = worst pain). This will be completed prior to the Investigator's injection site assessment.

ISAF population will be used for all subject injection site pain score summaries.

Subject injection site pain score will be categorized as follows:

- 0 = No pain
- 1-3 = Mild pain
- 4-6 = Moderate pain
- 7-10 = Severe pain

The following summaries will be provided for subject injection site pain score data.

- Descriptive Statistics for the pain score (0-10) by treatment and scheduled timepoint.
- Frequency and percentage of the pain score categories (no pain, mild pain, moderate pain and severe pain) by treatment and scheduled timepoint.
- Data listing of subject injection site pain score.

### **18.6.3. COLUMBIA-SUICIDE SEVERITY RATING SCALE (C-SSRS)**

The C SSRS is a tool designed to systematically assess and track suicidal AEs (suicidal behavior and suicidal ideation) throughout the study. The strength of this suicide classification system is in its ability to comprehensively identify suicidal events while limiting the over-identification of suicidal behavior

This study utilizes 2 versions of the C-SSRS, the Screening/Baseline version and at the Since Last Visit version. The Screening/Baseline version consists of "Lifetime" Questionnaire and "Past 1 Month" Questionnaire, where Since Last Visit version consists of "Lifetime" Questionnaire.

Screening Baseline version will be administered at Screening Visit, where Since Last Visit version will be administered at the subsequent visits.

Summary of C-SSRS will be presented for the ISAF population. OSAF population will be used for the listing.

---

Document:

Author:

Version Number:  
Version Date:

Final Draft  
11APR2019

Template No: CS\_TP\_BS016 Revision 4  
Effective Date: 01Apr2016

Reference: CS\_WI\_BS005

